5.2.4. Maintained FVC Response

Subjects with follow-up FVC%pred measurements at or above their baseline FVC%pred level will be classified as having maintained FVC response. Subjects with reduced FVC%pred levels or missing data for any reason, including death or medical frailty, will be classified as having not maintained FVC response. The FVC%pred value is used because unadjusted FVC measurements are expected to decline with age.

6. Safety Evaluations and Procedures

6.1. Adverse Events

During a clinical trial, the reporting of adverse experience information can lead to important changes in the way a new treatment is developed, as well as provide integral safety data.

6.1.1. Definitions

An **adverse event (AE)** is any untoward medical occurrence in a subject or clinical investigation subject who was administered a pharmaceutical product. The AE does not necessarily have to have a causal relationship with the drug administered. An AE can be any unfavorable and unintended sign (including an abnormal laboratory finding), symptom, or disease temporarily associated with the use of a medicinal product, whether or not considered to be related to the medicinal product. Diseases, signs, symptoms, or laboratory abnormalities already existing at enrollment are not considered AEs unless they worsen (ie, increase in intensity or frequency). Surgical procedures themselves are not AEs; they are therapeutic measures for conditions that require surgery. The condition for which the surgery is required may be an AE. Surgical procedures planned before randomization and the conditions necessitating the surgery are not AEs.

A **serious adverse event** is any untoward event that:

- Is fatal
- Is life-threatening
- Requires inpatient hospitalization or prolongation of existing hospitalization, with the following exceptions:
 - Preplanned (before the study) hospital admissions, unless the hospitalization is prolonged
 - Planned admissions (as part of a study, eg, routine biopsies)
 - Hospitalization lasting < 24 hours

- Hospitalization for elective procedure
- Emergency room visits
- Results in persistent or significant disability or incapacity
- Is a congenital anomaly or birth defect
- Important medical events that may not result in death, be life-threatening, or require inpatient hospitalization may be considered serious adverse events (SAEs) when, based on appropriate medical judgment, they may jeopardize the subject and may require medical or surgical intervention to prevent one of the outcomes listed above.

Life-threatening means that the subject was, in the view of the investigator, at immediate risk of death from the AE as it occurred. It does not include an AE that, had it occurred in a more severe form, might have caused death.

Persistent or significant disability/incapacity means that the event resulted in permanent or significant and substantial disruption of the subject’s ability to carry out normal life functions.

Causality:

A reasonable possibility means the AE may have been caused by/related to the study drug. A perceived or real lack of efficacy does not satisfy the definition of relatedness.

6.1.2. Adverse Event (AE) Reporting

For the PANTHER-IPF trial, all AEs (serious and nonserious), occurring from randomization through final study visit (4 weeks after final dose of all study medication) will be recorded on the AE page of the case report form (CRF)

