4.4. Study Design and Study Visit

4.4.1. Study Design Summary

This study will be a randomized, double-blind, PL-controlled trial designed to assess the safety and efficacy of NAC in subjects with newly diagnosed IPF.

Subjects with mild to moderate IPF (defined as $FVC\%pred \geq 50\%$ and $DLCO\%pred \geq 30\%$) diagnosed within the past 48 months will be enrolled. Screening will continue until April 30, 2012.

The study will employ a 2-arm design with 1:1 randomization to NAC or PL. Once enrolled, subjects will visit the clinical center at 15 weeks and 15-week intervals thereafter. Each subject will be treated and followed for a maximum of 60 weeks.

During the 60-week visit, subjects will be taken off all study agents. Approximately four weeks after the final dose of study agent is taken, subjects will receive a safety phone call from the study site.

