4.4.2.8. Final Visit – Telephone Follow-up

Four weeks following the final dose of study medication, subjects will receive a telephone call from the study coordinator to ensure that there are no side effects and to follow up on any ongoing adverse events (AEs).

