4.4.2.9. Phone Contact Between Visits

At week 2 and each month that a subject does not have a scheduled clinical center visit, his or her study coordinator will contact him or her at least once by telephone to:

- Inquire if the subject has had any hospitalizations, events that might be considered an AE, or any events significant enough to warrant an out-of-cycle visit to the clinical center.
- Remind subjects of their current dosage levels and confirm that the subject understands them.
- Address any questions or concerns the subject might have regarding other aspects of the study.
- Assess adherence to the treatment regimen by reviewing diary data; verbal review of medications taken, including nutritional supplements.

Table 3: Schedule of Assessments

Procedure	Screening Visit 0	Enrollment Visit 1	Week 15 Visit 2	Week 30 Visit 3	Week 45 Visit 4	Week 60 / Early Withdrawal Visit 5	Final ¹ Visit (via phone)
Informed consent	X						
Medical history	X						
Inclusion/exclusion criteria	X						
Serum pregnancy test (if applicable)	X	X	X	X	X		
Review of lung biopsy	X						
Arterial Blood Gas	X					X	
6-Minute Walk Test				X		X	
Physical examination	X			X		X	
Vital signs with oximetry	X	X	X	X	X	X	
Body height and weight	X	X	X	X	X	X	
Complete Blood Count	X			X		X	
Chemistry panel	X			X		X	
Monitor Lab Values	X			X		X	
Urinalysis	X						
Specimen repository substudy blood draw and urine collection (if consented)			X	X	X	X	
HRCT (if not completed within three months)	X						
Spirometry (pre- and post-bronchodilator)	X						
Spirometry (post-bronchodilator only)		X	X	X	X	X	
DLCO (post-bronchodilator only)	X			X		X	
Lung volumes (post-bronchodilator only)	X						
Evaluate for acute exacerbation		X	X	X	X	X	
Review Adverse Events		X	X	X	X	X	X
Review concomitant meds	X	X	X	X	X	X	
Dispense subject diary		X	X	X	X		
Review subject diary		X	X	X	X	X	
Dispense study agent		X	X	X	X		
Gender Substudy questionnaire (female subjects only)		X					
EuroQoL, ICECAP, UCSD SOBQ, SGRQ, SF-36		X		X		X	

Abbreviations: DLCO, diffusing capacity of the lung for carbon monoxide; QoL, Quality of Life; ICECAP, Investigating Choice Experiments for Preferences of Older People; UCSD SOBQ, University of California Shortness of Breath Questionnaire; SGRQ, St. George's Respiratory Questionnaire; SF-36, Short Form 36 Health Survey

¹Follow-up visit via phone will occur four weeks after final dose of study medication

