4.5. Dose Justification

The general philosophy for determining dosing levels was to apply previously examined treatment regimens. With the focus of the study being to establish a standard of care for mild/moderate IPF subjects, the goal was to develop flexible yet standardized treatment rules that allow for the temporary or permanent withholding of one or more components of treatment when necessary. Subjects developing laboratory abnormalities or symptoms that result in discontinuation of one or more components of study treatment may continue on the other components as long as there is no contraindication for this. Complete follow-up is important for the validity of any study. As a strategy to maintain protocol adherence, we are using a treatment regimen that will detect potential side effects and prompt interventions proactively in the interest of patient safety. In addition, subjects who permanently stop study medications during the course of the study are encouraged to continue in the study, completing all scheduled visits and tests.

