6.1.2.1. Serious Adverse Events (SAE) Reporting

For this trial, all deaths and all SAEs, which occur from randomization through final study visit, must be entered within the EDC system, via the SAE eCRF page within 24 hours of the investigative site’s knowledge of the event. It is the responsibility of the clinical center

investigator to provide a causality assessment of the event for each study medications based upon the information available at the time of the report. It is understood that complete information about the event may not be known at the time the initial report is submitted. In the event the EDC system is not accessible to the site at the time of event reporting, investigative sites will complete and forward a paper back-up SAE form to DCRI Safety Surveillance for processing:

DCRI Safety Surveillance

[contact] or [name] (toll free)

[contact] or [name] (toll free)

The investigator must complete and submit follow-up SAE information via the eCRF when important new or follow-up information (e.g., final diagnosis, outcome, results of specific investigations) becomes available. Follow-up information should be submitted according to the same process used for reporting the initial event as described above. All SAEs will be followed until resolution, stabilization, or 30 days after the subject has completed the final visit (4 weeks after the final dose of study medication), whichever occurs first. The investigator is responsible for reporting SAEs to their institutional review board (IRB) per site specific IRB reporting guidelines.

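### The recording window for adverse events, SAEs and deaths is tied to the last dose, which contradicts the follow-up schedule for subjects who stop drug early but stay in the study

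*Protocol*

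**What the plan says.** Section 6.1.2 (Adverse Event Reporting) states that all AEs, serious or not, "occurring from randomization through final study visit (4 weeks after final dose of all study medication) will be recorded" on the AE page.

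Section 6.1.2.1 (SAE Reporting) requires that "all deaths and all SAEs, which occur from randomization through final study visit, must be entered within the EDC system", within 24 hours of the site learning of the event. Later in the same section, SAEs are to be followed to resolution, stabilization or "30 days after the subject has completed the final visit (4 weeks after the final dose of study medication), whichever occurs first".

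Section 4.4.2.8 (Final Visit – Telephone Follow-up) gives the same timing: "Four weeks following the final dose of study medication, subjects will receive a telephone call from the study coordinator". The footnote to Table 3 agrees.

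On follow-up, section 4.4.1 says "Each subject will be treated and followed for a maximum of 60 weeks". Section 4.5 adds that "subjects who permanently stop study medications during the course of the study are encouraged to continue in the study, completing all scheduled visits and tests". Section 4.5.1.2 foresees permanent discontinuation for gastrointestinal or skin reactions.

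Table 3 has a row "Review Adverse Events" marked at every visit from enrollment to week 60 and at the final phone visit. Section 4.4.2.9 sets a call at week 2 and in each month without a clinic visit, asking about hospitalizations and possible AEs. Section 5.2.2 has all subjects telephoned monthly about dyspnea, cough, clinic visits and hospitalizations. None of these contacts is limited to subjects still on drug.

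**The concern.** For a subject who takes drug to week 60, the final visit and the point 4 weeks after the last dose coincide at about week 64, and the rule works. For a subject who stops permanently at, say, week 15 and stays, the final study visit has two possible dates: week 19 by the stated definition, or the end of participation at week 60 or later by the visit schedule. The protocol does not say which governs recording.

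Mortality, time to death, AEs and hospitalizations are secondary goals in section 2.3, and death is a component of time to disease progression in section 5.2.1. Safety is half of Specific Aim 1. If one site enters a death or hospitalization at week 40 in an early stopper and another site, following section 6.1.2 to the letter, does not, these comparisons rest on uneven capture. Because the protocol names gastrointestinal and skin reasons to stop, stopping could be more frequent on NAC than on placebo, and any under-capture could then differ by arm.

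**Working it through.** The plan gives no figure on this point, so there is none to reproduce. The primary FVC comparison and its power do not depend on the recording window. The check sets the passages side by side and then does the window arithmetic.

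**Passages.** Three places define the final visit as 4 weeks after the final dose: section 6.1.2, the SAE follow-up rule in section 6.1.2.1, and section 4.4.2.8 (with the Table 3 footnote). Against them, section 4.5 keeps permanent stoppers in scheduled follow-up, and Table 3 and sections 4.4.2.9 and 5.2.2 keep asking about events. No passage says that AE pages, or SAE and death entry, continue past 4 weeks after an early last dose.

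**Per subject.** Inputs: window end = last dose + 4 weeks (section 6.1.2); follow-up to week 60 (section 4.4.1). With the last dose at week t, follow-up outside the literal window is max(0, 60 − (t + 4)) = max(0, 56 − t) weeks.

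| Last dose (week) | Literal window ends (week) | Weeks outside, to week 60 | Share of 60 weeks |
|---|---|---|---|
| 2 | 6 | 54 | 90% |
| 15 | 19 | 41 | 68% |
| 30 | 34 | 26 | 43% |
| 45 | 49 | 11 | 18% |
| 56 or later | 60 or later | 0 | 0% |

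**Whole trial, illustration only.** The protocol gives neither the rate nor the timing of permanent discontinuation. Assume that stop times are uniform over 60 weeks and that every stopper stays to week 60. The mean time outside the window per stopper is then

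∫₀⁵⁶ (56 − t)/60 dt = 56²/120 = 26.1 weeks.

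Planned follow-up is 260 × 60 = 15,600 person-weeks (about 130 per arm, Protocol Summary).

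| Assumed share stopping and staying | Subjects | Person-weeks outside | Share of 15,600 |
|---|---|---|---|
| 5% | 13 | 340 | 2.2% |
| 10% | 26 | 679 | 4.4% |
| 20% | 52 | 1,359 | 8.7% |
| 30% | 78 | 2,038 | 13.1% |

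These are upper figures for each assumed rate. Some stoppers will leave the study, and some sites will enter late events anyway.

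**After the fix.** If the window runs to the later of 4 weeks after the final dose and the end of participation, the time outside it is 0 weeks for any t.

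**The case against.** The best defence is that the parenthesis in section 6.1.2 simply describes the ordinary completer. A contact at week 19 is not the final visit of someone who attends at weeks 30, 45 and 60. In section 6.1.2.1 the sentence that creates the duty to enter deaths and SAEs says only through the final study visit; the last-dose gloss comes later, in the rule on following SAEs. On that reading nothing is lost, and the continuing AE reviews and monthly calls show what was meant.

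Much of this stands, and it rules out several stronger conclusions that a reader might draw:

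- *That event collection closes for early stoppers.* The documents do not establish this. Enquiry continues to week 60 whatever the drug status, death counts toward a secondary efficacy endpoint that has no last-dose cut-off, and section 9.2 plans to report vital status in the flow diagram.
- *That acute exacerbations are lost in the same way.* Section 5.2.2 gives them a required case report form of their own and sends suspected cases to adjudication, neither tied to the last dose. They are less exposed.
- *That a promised intention-to-treat safety analysis is undermined.* Section 9.1 states that principle for the primary analyses. Section 9.2 bases safety on randomized subjects who took at least one dose.
- *That a number of missed deaths can be given.* The protocol states neither a mortality nor a discontinuation rate.

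What the defence does not remove is the contradiction. Asking about an event is not a duty to record it. The recording duty sits in sections 6.1.2 and 6.1.2.1, and the only definition of its end point that the protocol offers is 4 weeks after the final dose. A site can follow that wording in good faith.

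**Conclusion.** The point holds as an internal contradiction about when AE, SAE and death recording ends for subjects who stop drug early and remain in follow-up. It does not show a decision to stop recording events in these subjects, and it does not show that events will in fact be missed.

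For an individual, the size follows from the protocol's own timings: 56 − t weeks outside the literal window, or 41 of 60 weeks for a stop at week 15. For the trial as a whole, the size cannot be determined. The illustrative 2.2% to 13.1% of planned person-time rests on assumed stopping in 5% to 30% of subjects, uniform stop times and full retention to week 60, whereas section 4.5 only encourages subjects to stay. A difference in capture between the arms is possible if stopping differs, but the protocol gives no rate by which to judge it. The primary FVC analysis is not affected.

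It is worth correcting while subjects are still in follow-up, since events not entered at the time are hard to recover later.

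**What to change.** In sections 6.1.2 and 6.1.2.1, define the recording window for AEs, SAEs and deaths as randomization through the later of (a) 4 weeks after the final dose and (b) the end of study participation, meaning the week-60 visit or the last study contact. Align the final-visit wording in the SAE follow-up rule, section 4.4.2.8 and the Table 3 footnote, so that the term has one meaning for subjects who stop drug early.

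The cost is a wording change, matching guidance to sites, and a small amount of extra event entry for subjects who stop early and stay. The visits, AE reviews and calls are already scheduled. Sample size and power do not change. The choice of analysis windows for these events can be left to the SAP.

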6.1.2.1. Serious Adverse Events (SAE) Reporting

For this trial, all deaths and all SAEs, which occur from randomization through final study visit, must be entered within the EDC system, via the SAE eCRF page within 24 hours of the investigative site’s knowledge of the event. It is the responsibility of the clinical center

investigator to provide a causality assessment of the event for each study medications based upon the information available at the time of the report. It is understood that complete information about the event may not be known at the time the initial report is submitted. In the event the EDC system is not accessible to the site at the time of event reporting, investigative sites will complete and forward a paper back-up SAE form to DCRI Safety Surveillance for processing:

DCRI Safety Surveillance

[contact] or [name] (toll free)

[contact] or [name] (toll free)

The investigator must complete and submit follow-up SAE information via the eCRF when important new or follow-up information (e.g., final diagnosis, outcome, results of specific investigations) becomes available. Follow-up information should be submitted according to the same process used for reporting the initial event as described above. All SAEs will be followed until resolution, stabilization, or 30 days after the subject has completed the final visit (4 weeks after the final dose of study medication), whichever occurs first. The investigator is responsible for reporting SAEs to their institutional review board (IRB) per site specific IRB reporting guidelines.

6.1.2.2. Regulatory Reporting

AEs that are serious, study drug related, and unexpected will be reported to the regulatory authorities. The DCRI Safety Surveillance medical monitor will perform a medical review of all SAEs submitted and evaluate for “unexpectedness.” DCRI Safety Surveillance will prepare MedWatch reports for those events identified as serious, study drug related and unexpected as determined by Safety Medical Monitor.

DCRI Regulatory Services will submit all unexpected, study drug-related SAEs as per 21 CFR 32. DCRI Safety Surveillance will provide a safety alert letter to the NHLBI, DSMB, and DCC clinical operation (for distribution to sites) within 15 days of initial receipt of the information.

Investigators are responsible for promptly reporting these events to their reviewing IRBs according to site specific IRB reporting guidelines.

6.2. Clinical Medical Monitoring

There will be an unblinded physician at the IPFnet DCC serving as medical monitor. The medical monitor will be available to assist with questions about dosage adjustments of study medications, including discontinuation or resumption of medications.

6.3. Unblinding Procedures

Unblinding of subjects or investigators to subject treatment is strongly discouraged. For ongoing clinical management, all subjects should be presumed to be receiving “active” study drug. To ensure the subject’s safety, the study treatment will be dose-adjusted based on laboratory test results, clinical findings, and symptoms.

The IPFnet DCC medical monitor and PANTHER-IPF co-chairs, Drs. [name] and [name], will be available to the study physicians to discuss study drug management on a case-by-case basis. Un-blinding will be considered ONLY when the knowledge of subject treatment assignment is ABSOLUTELY ESSENTIAL for subject safety and after discussion of the subject’s case with the medical monitor and either [name] or [name]. Unblinding of study treatment should be minimized during the conduct of the trial. In those cases where it is felt to be medically necessary the DCC medical officer will communicate directly with the managing physician to minimize unblinding of study personnel.

7. Study Drug Procedures

At the baseline, 15-week, 30-week, and 45-week study visits, subjects will receive a supply of study drug sufficient to last until the next visit at which study drug will be dispensed.

8. Data Management

8.1. Hardware and Software Configuration

8.1.1. Hardware and Database Software

Data will be stored in an Oracle database system. Oracle has advantages of processing efficiency and smooth linkage with other software systems. The application and database will be hosted on Solaris Unix servers at the IPFnet DCC.

8.1.2. Statistical Software

SAS will be used as the principal application for the management of analysis data files and statistical computations. S-Plus will be used to provide supplementary functions as needed.

8.1.3. Access Control and Confidentiality Procedures

Access to databases will be controlled centrally by the IPFnet DCC through user passwords linked to appropriate privileges. This protects the data from unauthorized changes and inadvertent loss or damage.

8.1.4. Security

Database and Web servers will be secured by a firewall and through controlled physical access. Oracle has many security features to ensure that any staff member accessing the database has the proper authority to perform the functions he or she requests of the system. Within the secondary SAS databases, Unix group-access control maintains similar security. The Sun workstation login is secured by extensive user-password facilities under Unix.

8.1.5. Back-up Procedures

Database back-up will be performed automatically every day, and standard IPFnet DCC policies and procedures will be applied to dictate tape rotation and retention practices.

8.1.6. Virus Protection

All disk drives that provide network services, and all user computers, will be protected using virus-scanning software. Standard IPFnet DCC policies will be applied to update these protection systems periodically through the study.

8.2. Sources of Data

8.2.1. Design and Development

The IPFnet DCC will be responsible for development of the electronic case report forms (eCRFs), development and validation of the clinical study database, ensuring data integrity, and training clinical center staff on applicable data management procedures. A web-based distributed data entry model will be implemented. This system will be developed to ensure that guidelines and regulations surrounding the use of computerized systems used in clinical trials are upheld. The remainder of this section provides an overview of the data management plan associated with this protocol.

